### **Concise Summary of Project.**

In the proposed research, we will enroll a total of 90 subjects over 16 weeks. Just as in the original AIM study (approved by UTSW IRB #072010-144), subjects will be randomly assigned to participate in one of 3 conditions with 30 subjects per group. Two of the groups involve active intellectual engagement. In these groups, novice subjects will engage in high-demand or moderate-demand photography in five hours of structured courses with professional instructors for each of the 16 weeks. Subjects will also be required to put in an additional investment of 10 hours each working on a project to which they can apply their learned skills. Subjects are expected to be working on their projects for a total of 210 hours of engagement over the 16 weeks. We will measure pre/post change in multiple measures of cognitive and neural function, affect, and activity over the 16 weeks, and contrast change with one control group. The control group, the Placebo Control, will engage alone at home in tasks that are relatively low in intellectual engagement such as listening to music and radio or completing work-books that rely primarily on activation of knowledge. Preliminary data collected at the University of Illinois has indicated that volunteers willingly engage in a similar program.

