### **Intervention (Weeks 3-16)**

Subjects will be pseudo-randomly assigned to intervention groups (based on gender and education criteria and the needs of the study) and then will participate for at most 14 weeks in the manipulation to which they were assigned. All will be told that there are numerous studies in the literature suggesting that the condition to which they were assigned is a form of engagement that has been shown to improve cognition. This is true, as many correlational studies have shown that engagement in tasks as passive as watching television is related to better cognition. All subjects will be required to agree to participate in any of the three conditions so that no condition will be biased. They will be novices at the use of the digital camera and will have had only minimal experience with computers, , or digital photography. Subjects who use traditional cameras will be permitted to enroll.

**Productive Engagement Groups.** (High-Demand and Moderate-Demand Photography) Sixty total participants will be assigned to one of the productive engagement groups (with thirty participants in each group): high-demand photography, and moderate-demand photography. Before the intervention begins, subjects will be provided equipment appropriate to their intervention for them to loan throughout the 12- to 14-week intervention. Participants in either of the photography groups will be supplied digital cameras. These 30 participants in each group may be separated further into smaller sections based on instructor availability in order to take advantage of smaller class sizes.

Each group will meet for 2.5 hours twice a week (5 hours per week total) at the research site. During this time, subjects will be stepped through a detailed curriculum by professional instructors, and those who learn techniques quickly will be pushed along so that maximum new learning occurs for each subject. Additionally, all subjects will be required to spend an additional 10 hours working on a special project at the research site without any formal instruction. This project is meant to provide participants with an opportunity to apply their skills to a task as they are learning. The high-demand photography group will learn similar skills as the moderate-demand photography group, but will learn them at a significantly quicker pace and, therefore, will learn more skills by the end of the intervention than the moderate-demand group.

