Based on our experience, we find that the final week of the interventions can be very busy and that some subjects experience somewhat lower affect in the last week due to their regrets that the class is ending. To ease this problem, we offer all subjects the opportunity to continue to work for at least two more weeks after the formal 12-week class is over, and subjects are paid sufficiently well to allow them to purchase a camera, should they desire to continue their work. Additionally, many subjects make plans for continued social relationships among group members.

**At-Home Engagement Group (Placebo Control).** Thirty subjects will be assigned to this group. Each participant will be given a personal DVD player, if they do not have one already, to borrow while they are enrolled in the study. Each week, subjects will come to the lab to maintain contact with the researchers and receive a new set of materials to work on that week. Subjects will be supplied with a range of stimulating activities to complete each week at home.

Subjects will have five hours of required activities each week and will select an additional 10 hours of activities of their choice from a provided list. For the five required hours, subjects will (1) watch 1 hour of humorous programming, (2) watch 1 hour of educational programming, (3) read 1 hour of an educational magazine, (4) listen to 1 hour of classical or world music, and (5) complete 1 hour of puzzle games that rely on activation of existing knowledge (such as crossword puzzles or handheld games). Subjects will then select the additional ten hours of activities which include (1) 2 hours of watching humorous programming of their choice, (2) 2 hours of watching educational programming and reading educational material, (3) 2 hours of listening to music CDs, (4) 2 hours of completing paper and pencil or handheld games, and (5) 2 hours of watching classical programming of their choice including Oscar-winning movies and movie classics. All participants will answer simple questions about the amount of time they spent on each task, how well they liked each task, and how it made them feel, including questions about whether it made them feel more alert.

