## Statistical Analysis Plan

Preliminary Analyses. In initial analyses, we will summarize categorical variables by proportions and continuous variables by means and quantiles. We will graph continuous variables and assess them for skewness, transforming if necessary (for example by logs or square roots) to render them more nearly normally distributed. We will explore relationships among variables by examining scatter plots and correlation matrices. We will conduct all analyses in R (version 3.3.2 or later) or SAS (version 9.4 or later).

Analysis of Primary Outcome Variables. The primary cognitive outcome endpoint will be a composite, scalar episodic memory score, as described in earlier research from the SYNAPSE project (5). This measure will exhibit substantial between-subject variability, in that subjects who give high scores at baseline are likely to give high scores at follow-up as well. To account for this, in primary analyses we will adjust for baseline levels by analysis of covariance — i.e., including baseline values together with treatment arm in a regression model for the post-treatment outcome. Alternatively (and equivalently), we can analyze the outcome variable in a mixed model, evaluating a treatment effect by estimating a time-by-treatment interaction. We will moreover conduct mixed-model analyses including the intermediate (6-week, mid-treatment) and long-term (1-year) values of the cognitive outcomes together with the end-of-treatment (12-week) outcome. As a secondary analysis to further elucidate the magnitude and timing of treatment effects, we will seek to create parsimonious models of this outcome as a function of time, treatment arm, stratification factors (center, age, sex, education) and potentially other factors measured at baseline. The primary brain outcome will be a vector measure of fMRI activation in four brain regions of interest, as described above and in previous work from SYNAPSE (7). This measure is also likely to exhibit substantial between-subject variability. We will again analyze the outcome variable in a mixed model, evaluating the treatment effect by estimating a time-by-treatment interaction, and conduct a secondary analysis where we model activation in the four regions as functions of time, treatment arm, stratification factors (center, age, sex, education) and potentially other factors measured at baseline.

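### Class delivery in the photography arms is not reflected in any planned model, so the standard errors for the arm contrasts may be too small

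*Combined protocol and SAP*

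**What the plan says.** **Allocation is individual.** The Concise Summary of Project says "subjects will be randomly assigned to participate in one of 3 conditions with 30 subjects per group".

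**Delivery differs by arm.** For the photography arms, Intervention (Weeks 3-16) says "Each group will meet for 2.5 hours twice a week (5 hours per week total) at the research site", and then "These 30 participants in each group may be separated further into smaller sections based on instructor availability". It adds that "all subjects will be required to spend an additional 10 hours working on a special project at the research site without any formal instruction", without saying whether those hours follow section lines. The same section notes that "many subjects make plans for continued social relationships among group members". For the third arm, the Concise Summary says "The control group, the Placebo Control, will engage alone at home in tasks that are relatively low in intellectual engagement"; Intervention (Weeks 3-16) adds a weekly lab visit for contact and materials.

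**Analysis.** The Statistical Analysis Plan describes the primary analysis as ANCOVA, "including baseline values together with treatment arm in a regression model for the post-treatment outcome". Its secondary models describe the outcome "as a function of time, treatment arm, stratification factors (center, age, sex, education) and potentially other factors measured at baseline". Under Latent Factor Modeling, the only dependence described is within a subject over time. The dose-response, subgroup and neuroimaging paragraphs name no class, section or instructor term either. The random effects of the mixed models are not listed, so for those models the absence of a class term is inferred from silence.

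The documents do not give the number of sections, which instructor teaches which arm, an ICC or alpha.

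**The concern.** This is a partially nested design: clusters form after randomisation in two of the three arms, and the third has none. Random allocation of individuals does not remove correlation that arises later from a shared instructor, shared pace or shared classmates. A model that treats all participants as independent then understates the variance of the photography arm means.

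The two contrasts are affected differently. Photography versus placebo is affected whoever teaches, because placebo has no class effect to offset it. High versus moderate is affected only by the part of the class effect that the two arms do not share. An instructor who teaches both arms cancels out of that comparison; peer effects in separate classes do not.

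These contrasts carry the stated aim of learning whether mental effort contributes to cognitive change (Purpose) and the dose-response analysis. The Purpose section also says these groups inform the feasibility of a full trial, so an overconfident contrast could carry forward into that decision. A center term, where used, does not stand in for class, because classes are nested within arm.

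**Working it through.** **Inputs from the documents.** 30 per arm (Concise Summary); 15% to 20% not completing at most (Incomplete data), so as few as 0.8 × 30 = 24 per arm; class delivery in two arms; model terms as listed in the SAP. The plan states no figure on this point that could be reproduced.

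**Assumed.** Two-sided 5% test; ICC of the baseline-adjusted outcome 0 to 0.05; 2 or 3 sections per arm, or one class if an arm is not split; baseline correlation 0.7 in the simulations.

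**Formulas** (n per arm, m per class, residual variance 1):
- Design effect in a photography arm: DE = 1 + (m − 1) × ICC. Placebo: 1.
- True variance, photography − placebo: (DE + 1)/n.
- True variance, high − moderate: 2 × (DE − s × m × ICC)/n, where s is the share of the ICC common to matching sections of the two arms.
- Variance the model reports: (2/n) × the pooled residual variance, whose expectation in a photography arm is (n − DE)/(n − 1).

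**Worked case: n = 30, two sections of 15, ICC 0.05, s = 0.**
- DE = 1 + 14 × 0.05 = 1.70.
- Reported: photography-arm residual variance (30 − 1.70)/29 = 0.976; pooled (2 × 0.976 + 1)/3 = 0.984; times 2/30 = 0.0656.
- True, photography − placebo: 2.70/30 = 0.0900. SE ratio √(0.0900/0.0656) = 1.17; false-positive rate 2 × [1 − Φ(1.96/1.17)] = 9.4%.
- True, high − moderate: 3.40/30 = 0.1133. SE ratio 1.31; false-positive rate 13.6%.

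**Simulation of the SAP's ANCOVA** (post on baseline and three arms, 100,000 trials per setting, 30 per arm, s = 0), false-positive rate:

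| ICC | Classes per arm | Photography − placebo | High − moderate |
|---|---|---|---|
| 0 | 2 / 3 | 5.0% / 5.0% | 5.0% / 5.1% |
| 0.01 | 2 / 3 | 5.8% / 5.7% | 6.7% / 6.0% |
| 0.02 | 2 / 3 | 6.6% / 6.0% | 8.4% / 7.0% |
| 0.05 | 2 / 3 | 9.4% / 7.7% | 13.3% / 10.4% |
| 0.05 | 1 | 13.9% | 21.2% |

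At ICC 0.01 the formula gives 5.9% and 5.5% for photography − placebo, so the small difference between 2 and 3 sections in that row is partly simulation error.

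**Sharing between arms, ICC 0.05, 2 / 3 sections.** High − moderate falls to 8.8% / 7.4% if half the ICC is shared and to 4.7% / 4.6% if all of it is. Photography − placebo stays at about 9% / 8%. Apart from a small term, the SE ratios are √(1 + (m − 1) × ICC × (1 − s)) and √(1 + (m − 1) × ICC/2). They are equal at s = 0.5, so high − moderate is the worse affected only if less than half the ICC is shared.

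**With 24 per arm, ICC 0.05, 2 / 3 sections.** Photography − placebo 8.3% / 7.2%. High − moderate 11.5% / 9.3% (none shared), 8.1% / 6.8% (half), 4.7% / 4.5% (all). One class per arm, none shared: 12.2% and 18.5%.

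**Does inflating the SE repair it?** With 2 to 3 sections and the true ICC, multiplying by √((DE + 1)/2) for photography − placebo gives 4.9 to 5.3%. Multiplying by √DE on the unshared ICC for high − moderate gives 4.5 to 5.3%. With one class per arm the rates are about 4.6 to 5.5%. Applying √DE to the total ICC of 0.05 when half or all of it is shared over-corrects high − moderate, to 2.8 to 3.5% or 1.0 to 2.0%.

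**The case against.** The strongest reply is that nothing in the documents shows a positive ICC. The primary outcome is a composite of standardised memory tests, not the photographic skill taught. Teaching follows a set curriculum with individual pacing, and 10 of the 15 weekly hours have no formal instruction. All of this points to a small ICC. At 0.01 to 0.02 with 2 to 3 sections, photography versus placebo is at most about 6.6%. The remark on continuing social ties comes from earlier experience and is no evidence that memory scores correlate within a class. This stands as a limit on size: only the direction follows from the design.

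Splitting into sections is only a possibility. That is true, but an unsplit arm is one class of 30, which gives the largest inflation and confounds class with arm completely. There the remedy is mainly a stated limitation, since a class term cannot be estimated.

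The SAP does not list its random effects, so a class term is unspecified rather than excluded. That is right for the mixed models; the ANCOVA's terms are spelled out.

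Finally, if inference is confined to these particular classes as delivered, the planned standard errors can stand. That too is right, but a difference could then not be credited to demand rather than to these classes. The plan does not say which inference is meant.

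**Conclusion.** The concern holds as a conditional statement. With positive within-class correlation, the planned standard errors are too small for photography versus placebo, and for high versus moderate to the extent that class effects are not shared. Averaged over classes the point estimates are not biased; their precision is overstated.

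The size rests on an assumed ICC, section count and alpha. Across ICC 0.01 to 0.05 with 2 to 3 sections of 30-participant arms, it runs from under one percentage point above nominal to 9.4% for photography versus placebo, and from about 6% to 13.3% for high versus moderate with nothing shared. If instructors teach both arms, the latter range is an upper bound.

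The study's feasibility role moderates the stakes. This should be corrected because the correction is cheap and section membership may not be recoverable later. Confidence is medium, since the documents give no ICC.

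**What to change.** 1. Record section and instructor for every photography participant.
2. Keep the planned ANCOVA and mixed models. Beside them, report the contrasts with standard errors inflated at fixed ICCs of 0, 0.02 and 0.05, using DE = 1 + (m − 1) × ICC and m = sum of squared section sizes ÷ arm n.
   - Photography versus placebo: multiply by √((DE + 1)/2).
   - High versus moderate: multiply by √DE if instructors differ between arms. If the same instructors teach both, report the range from the planned SE (all shared) to √DE (none shared), and label √DE an upper bound.
   - Compute any tipping ICC with the fitted model's residual df. For example, with 24 per arm, m = 12 and 68 df (critical t 1.995), an illustrative t of 2.2 for high versus moderate tips at ((2.2/1.995)² − 1)/11 = 0.020; for photography versus placebo the tipping value is twice that, 0.039 before rounding.
3. Fit a partially nested model (random section effect in the photography arms only, small-sample df) as a supporting analysis only, and only if there are enough sections. With 2 to 3 sections per arm it leaves about 2 to 4 df for high versus moderate, and a 95% half-width of 1.24 or 0.80 SD even at ICC 0.
4. State whether inference is to these classes or beyond them. With one class per arm, or instructors confined to one arm, state that a class or instructor effect cannot be separated from the high-moderate difference.

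**Cost.** Two recorded variables and one table; the weekly instructor ratings described under Subject Diaries may already identify the instructor. No extra participants or staff, and no change to teaching.

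Reported intervals widen. With 24 per arm and 2 to 3 sections, the 95% half-width in baseline-adjusted SD units starts at 1.995 × √(2/24) = 0.58. At ICC 0.02 / 0.05 it becomes 0.60-0.61 / 0.62-0.65 for photography versus placebo, and 0.62-0.64 / 0.67-0.72 for high versus moderate.

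The inflated test is conservative if the assumed ICC is too high. Assuming 0.05 when the truth is 0 gives 2.8 to 3.4% versus placebo, and 1.5 to 2.3% for high versus moderate when the unshared ICC is 0.

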### **Mid-Intervention Cognitive Behavioral Battery: (Weeks 8-9)**

Mid-way through the intervention period, participants will be asked to complete the cognitive battery again (found in full in Appendix A). This will help with statistical analysis, specifically growth curve analysis.

### **Post-Intervention Test (Weeks 15-16)**

In the final two-weeks, participants will repeat their cognitive testing and take-home questionnaires. In addition, if they had an MRI session at pre-test, subjects will be asked to repeat the neuroimaging portion of the study as well.

### **Subject Compensation**

All subjects will be compensated \$75 each time they complete the behavioral testing (pre-testing, mid-testing, and post-testing) for a cognitive testing total of \$225. Subjects will receive \$50 compensation for completing the take-home questionnaire at pre-test and an additional \$50 for completing the take-home questionnaires at post-test (\$100 total). Subjects who are eligible and complete an MRI session will also be compensated \$100 for each MRI scan session completed (pre-test and post-test) for an MRI scanning total of \$200. Subjects will be compensated an additional \$75 if they complete all 3 months of the study. If subjects complete all possible sessions in the study, they will be compensated \$600.

### **Criteria for the Inclusion of Participants.**

- Participants must be adults between 60 and 90 years old.
- At least 35% of participants will be men, and at least 15% will be minorities.
- 10th grade education or higher is required
- Fluent in English
- ADAS-COG score of zero (a perfect score).
- A score of 18 or higher on the Barthel Index of Daily Functioning.
- Right-handed for MRI scanning.

### **Criteria for the Exclusion of Participants.**

- MMSE score lower than 27\*
- TICS score lower than 27
- Depression based on CESD screening (a score of 27 or greater)
- Major psychiatric or neurological disorder
- Chemotherapy presently or in past year
- Coronary bypass presently or in past year
- History of major substance abuse
- History of central nervous system disease or brain injury
- Corrected vision poorer than 20/40 on Snellen Eye Chart after correction
- Recreational drug use in past six months
- Conditions which would contra-indicate MRI: Prior surgeries and/or implant of pacemakers, pacemaker wires, artificial heart valve, brain aneurysm surgery, middle ear implant, non-removable hearing aid or jewelry, braces or extensive dental work, cataract surgery or lens implant, implanted mechanical or electrical device, artificial limb or joint; foreign metallic objects in the body such as bullets, BB's, shrapnel, or metalwork fragments; pregnancy, vertigo, claustrophobia, left handedness, BMI > 35, uncontrollable shaking, or inability to lie still for one hour.
- More than minimal experience with photography during the last 12 years
- Work at a structured job/volunteer more than 10 hours per week
- Computer experience that involves more than internet surfing and email
  
- Use of electronic devices to shop, pay bills, bank, and perform other higher-order functions
- Extensive experience with digital photography or post processing photo programs

These exclusion criteria omit individuals who do not possess sufficient skills or health to contribute useful data to the study. Individuals must meet some (relatively low) cognitive criterion to be able to complete the cognitive tasks. Individuals who are in extremely poor health (either physical or psychiatric) will not have sufficient resources to participate in the sustained nature of this resource. The exclusion criteria regarding past experience in digital photography, or sustained computer work are required so that participants are novices on the to-be-trained skills and the effects of sustained intellectual engagement can be assessed.

\*There is evidence in the literature that an MMSE score of 18 or greater provides participants with sufficient capacity for informed consent (Gregory et al., 2007). In an abundance of caution, we will exclude anyone from the study who does not have an MMSE over 26, eight points higher than that recommended in Gregory et al. (2007), in order to ensure that all participants are capable of giving consent. The MMSE will be used for screening criteria for all participants, given before the cognitive and psychosocial testing begin, in order to ensure participants are able to consent to the study.

### **Sources of Research Material.**

Information collected in the study from subjects and responses provided by subjects will be used for research. No materials will be used from medical records or other medical data. All data is obtained exclusively for research purposes. All data will be stored on a password protected, HIPAA-secure server in the PI's lab at the Center for Vital Longevity. All

data files, both behavioral and neuroimaging, will be coded by numbers, with no linkage to subject identity except via a password-protected file that is not directly linked to the data files.

